8.7. Pharmacokinetic Analysis

Descriptive summary statistics will be provided by treatment and visit/sampling timepoint with descriptive statistics (n, mean, SD, median, min, and max) at each timepoint by treatment. An exception to this is T_{max} where median, minimum and maximum will be presented.

Concentrations below the lower limit of quantitation (LLOQ) will be treated as zero in summary statistics and for PK parameter calculations. A geometric mean will not be reported if the dataset includes zero values.

Individual total MAA868 plasma concentration data will be listed by treatment (MAA868 arms only), subject, and visit/sampling timepoint. PK parameters will also be listed by treatment and subject.

8.8. Biomarkers

Coagulation parameters, including free and total FXI, FXI:C, and immunogenicity will be summarized by timepoint and treatment.

8.9. Interim Analysis (IA)

Safety and tolerability data (AEs, laboratory assessments, vital signs and ECG data) will be evaluated from Cohort 1 by the Sponsor's Medical Monitor and Covance Lead Project Physician after approximately 10 of the patients in cohort 1 have received their second dose of study drug and have been followed for at least an additional 14 days. The decision to proceed to cohort 2 will be made only after it is confirmed that the cohort 1 dose was safe and well tolerated, and the Sponsor determines there is adequate data to proceed to cohort 2. If notable AEs or safety concerns are found in cohort 1, the study may be terminated.

Likewise, after approximately 10 of the patients in cohort 2 have received their second dose of study drug and have been followed for at least an additional 14 days, safety, tolerability, and other analyses will be evaluated.

Additional IAs may be conducted to support decision making at any time concerning the current clinical study, the Sponsor's clinical development projects in general or in case of any emergent safety concerns. The Investigator(s) may be included for decisions with regards to any unplanned IAs that address questions of subject safety.

Unblinded IA results will be reviewed by the Sponsor (or their designees).

No further dissemination of interim results should occur, in particular not with individuals involved in treating the study's subjects or assessing clinical data (e.g. ECGs, symptoms) obtained in the study.

8.10. Data Quality Assurance

Site monitoring

Before study initiation, at a site initiation visit or at an investigator's meeting, a Covance representative will review the protocol and CRFs with the Investigator(s) and their staff. During the study Covance employs several methods of ensuring protocol and GCP compliance and the quality/integrity of the sites' data. The monitor will visit the site to check the completeness of subject records, the accuracy of entries on the CRFs, the adherence to the protocol and to GCP, the progress of enrollment, and ensure that study drug is being stored, dispensed, and accounted for according to specifications. Key study personnel must be available to assist the monitor during these visits.

The Investigator must maintain source documents for each subject in the study, consisting of case and visit notes (hospital or clinic medical records) containing demographic and medical information, laboratory data, electrocardiograms, and the results of any other tests or assessments. All information on CRFs must be traceable to these source documents in the subject's file. The Investigator must also keep the original informed consent form signed by the subject (a signed copy is given to the subject).

The Investigator must give the monitor access to all relevant source documents to confirm their consistency with the CRF entries. Covance monitoring standards require full verification for the presence of informed consent, adherence to the eligibility criteria, documentation of SAEs, and the recording of data that will be used for all primary and safety variables. Additional checks of the consistency of the source data with the CRFs are performed according to the study-specific monitoring plan. No information in source documents about the identity of the subjects will be disclosed.

Data collection

Designated Investigator staff will enter the data required by the protocol into the Electronic Case Report Forms using fully validated software that conforms to 21 CFR Part 11 requirements. Designated investigator site staff will not be given access to the electronic data capture (EDC) system until they have been trained. Automatic validation programs check for data discrepancies and, by generating appropriate error messages, allow the data to be confirmed or corrected before transfer of the data to Covance working on behalf of Anthos. The Investigator must certify that the data entered into the Electronic Case Report Forms are complete and accurate. After database lock, the Investigator will receive copies of the subject data for archiving at the investigational site.

Data not requiring a separate written record are noted on the Assessment schedule ([Table 9](#)) and can be recorded directly on the CRF. All other data captured for this study will have an external originating source (either written or electronic) with the CRF not being considered as source.

All data should be recorded, handled and stored in a way that allows its accurate reporting, interpretation and verification.

Database management and quality control

Covance will review the data entered into the eCRFs by investigational staff for completeness and accuracy and instruct the site personnel to make any required corrections or additions. System queries are sent to the investigational site using an electronic data query which will appear in eCRF once data have been entered and saved. Manual queries will be raised by Data Management in eCRF based ongoing manual review. Designated investigator site staff is required to respond to the query in the eCRF and confirm or correct the data.

Concomitant medications entered into the database will be coded using the WHO Drug Reference List, which employs the Anatomical Therapeutic Chemical classification system. Medical history/current medical conditions and adverse events will be coded using the Medical dictionary for regulatory activities (MedDRA) terminology.

Laboratory samples will be processed centrally, and the results will be sent electronically to Covance.

At the conclusion of the study, the occurrence of any emergency code breaks will be determined after return of all code break reports and unused drug supplies to Covance.

The occurrence of any protocol deviations will be determined. After these actions have been completed and the database has been declared to be complete and accurate, it will be locked, and the treatment codes will be unblinded and made available for data analysis. Any changes to the database after that time can only be made by joint written agreement between the Anthos Head of Regulatory and the Chief Medical Officer.

9. ETHICAL CONSIDERATIONS

9.1. Regulatory and ethical compliance

This clinical study was designed and shall be implemented, executed and reported in accordance with the ICH Harmonized Tripartite Guidelines for GCP, with applicable local regulations (including European Directive 2001/20/EC, US Code of Federal Regulations Title 21, and Japanese Ministry of Health, Labor, and Welfare), and with the ethical principles laid down in the Declaration of Helsinki.

9.2. Responsibilities of the Investigator and IRB

Before initiating a trial, the Investigator/institution must obtain approval/favorable opinion from the IRB for the trial protocol, written informed consent form, consent form updates, subject recruitment procedures (e.g. advertisements) and any other written information to be provided to subjects. Prior to study start, the Investigator is required to sign a protocol signature page confirming his/her agreement to conduct the study in accordance with these documents and all of the instructions and procedures found in this protocol and to give access to all relevant data and records to Covance monitors, auditors, Covance Quality Assurance representatives, designated agents of Anthos, IRBs, and regulatory authorities as required. If an inspection of the clinical site is requested by a regulatory authority, the Investigator must inform Anthos immediately that this request has been made.

For multi-center trials, a Coordinating Investigator will be selected by Anthos around the time of Last Patient Last Visit to be a reviewer and signatory for the CSR.

9.3. Publication of study protocol and results

The key design elements of this protocol will be posted in a publicly accessible database such as clinicaltrials.gov. Upon study completion and finalization of the study report the results of this trial will be posted in a publicly accessible database of clinical trial results in accordance with local regulations.

No publication or disclosure of study results will be permitted except under the terms and conditions of a separate written agreement between the Sponsor and the investigator and/or the investigator's institution.

The information developed from this clinical study will be used by the Sponsor in connection with the development of MAA868 and other drugs and diagnostics, and thus may be disclosed as required to other clinical investigators, business partners, or regulatory agencies. To permit the information derived from the clinical studies to be used, the investigator is obligated to provide the Sponsor with all data obtained in the study.

10. PROTOCOL ADHERENCE

This protocol defines the study objectives, the study procedures and the data to be collected on study participants. Additional assessments required to ensure safety of subjects should be administered as deemed necessary on a case by case basis. Under no circumstances is an Investigator allowed to collect additional data or conduct any additional procedures for any research related purpose involving any investigational drugs under the protocol.

Investigators ascertain they will apply due diligence to avoid protocol deviations. If an Investigator feels a protocol deviation would improve the conduct of the study this must be considered a protocol amendment, and unless such an amendment is agreed upon by Anthos and approved by the IRB and health authorities, where required, it cannot be implemented.

10.1. Protocol Amendments

Any change to the protocol can only be made in a written protocol amendment that must be approved by Anthos, Health Authorities where required, and the IRB prior to implementation.

Amendments that are intended to eliminate an apparent immediate hazard to subjects may be implemented immediately, provided the Health Authorities are subsequently notified by protocol amendment and the reviewing IRB is notified.

Notwithstanding the need for approval of formal protocol amendments, the Investigator is expected to take any immediate action required for the safety of any subject included in this study, even if this action represents a deviation from the protocol. In such cases, the reporting requirements identified in [Section 7.6.2](#) (Safety Monitoring) must be followed and the Study Lead informed.

12. APPENDICES

12.1. Appendix 1 - Liver Event Definitions and Follow-up Requirements

Table 4: Liver Event and Liver-Related Laboratory Alert Definition

Definition	Thresholds
Potential Hy's law cases	
 ALT or AST > 3 X ULN and TBL > 2 × ULN without initial increase in ALP to > 2 × ULN
ALT or AST elevation with coagulopathy	
 ALT or AST > 3 × ULN and INR > 1.5 (in the absence of anticoagulation)
ALT or AST elevation accompanied by symptoms	
 ALT or AST > 3 × ULN accompanied by (general) malaise, fatigue, abdominal pain, nausea, or vomiting, or rash, or eosinophilia
Isolated ALT or AST elevation	
 ALT or AST > 8 × ULN 5 x ULN < ALT/AST ≤ 8 x ULN 3 x ULN ALT/AST 5 x ULN
Isolated ALP elevation	
 ALP > 2 × ULN (in the absence of known bone pathology)
Others	
 Any clinical event of jaundice (or equivalent term) Any adverse event potentially indicative of liver toxicity

Table 5: Action required for Liver Events and Liver-Related Laboratory Alerts

Criteria	Action required
Potential Hy's law cases ALT or AST elevation with coagulopathy ALT or AST elevation accompanied by symptoms Isolated ALT or AST elevation > 8 X ULN Jaundice	
 Hospitalize, if clinically appropriate Establish causality Complete CRFs per liver event guidance
Isolated ALT or AST elevation > 5 to ≤ 8 X ULN	
 Establish causality Complete CRFs per liver event guidance
Isolated ALT or AST elevation > 3 to ≤ 5 × ULN (patient is asymptomatic)	
 Monitor liver chemistry tests two or three times weekly
Isolated ALP elevation	
 Repeat liver chemistry tests within 48-72 hours If elevation is confirmed, measure fractionated ALP; if >50% is of liver origin, establish hepatic causality Complete CRFs per liver event guidance
Any AE potentially indicative of liver toxicity	
 Hospitalize if clinically appropriate Complete CRFs per liver event guidance

Table 6: Exclusion of underlying Liver Disease

Disease	Assessment
Hepatitis A, B, C, E	
 • IgM anti-HAV; HBSAg, IgM anti-HBc, HBV DNA; anti-HCV, HCV RNA, IgM & IgG anti-HEV, HEV RNA
CMV, HSV, EBV infection	
 • IgM & IgG anti-CMV, IgM & IgG anti-HSV; IgM & IgG anti-EBV
Autoimmune hepatitis	
 • ANA & ASMA titers, total IgM, IgG, IgE, IgA
Alcoholic hepatitis	
 • Ethanol history, γGT, MCV, CD-transferrin
Nonalcoholic steatohepatitis	
 • Ultrasound or MRI
Hypoxic/ischemic hepatopathy	
 • Medical history: acute or chronic CHF, hypotension, hypoxia, hepatic venous occlusion. Ultrasound or MRI
Biliary tract disease	
 • Ultrasound or MRI, ERCP as appropriate
Wilson disease	
 • Caeruloplasmin
Hemochromatosis	
 • Ferritin, transferrin
Alpha-1-antitrypsin deficiency	
 • Alpha-1-antitrypsin

12.2. Appendix 2 - Specific Renal Alert Criteria and Actions

Table 7: Specific Renal Alert Criteria and Actions

Criteria	Action required
Serum creatinine (sCr) increase 25 – 49% compared to baseline	
 • Consider causes and possible interventions • Follow up within 2-5 days
Serum creatinine increase \geq 50%	
 • Consider causes and possible interventions • Repeat assessment within 24-48 hours if possible • Consider hospitalization and specialized treatment
Protein-creatinine or albumin-creatinine ratio increase \geq 2-fold, or new onset proteinuria \geq 1+ , or Albumin-creatinine ratio (ACR) \geq 30 mg/g or \geq 3 mg/mmol, or Protein-creatinine ratio (PCR) \geq 150 mg/g or $>$ 15 mg/mmol	
 • Consider causes and possible interventions • Assess serum albumin and serum protein • Repeat assessment to confirm
New onset glucosuria on urine exam (unless related to concomitant treatment, diabetes)	
Assess and document:
 
 • Blood glucose (fasting) • Serum creatinine • Urine albumin-creatinine ratio
New hematuria on urine exam	
Assess and document
 
 • Urine sediment microscopy • Assess sCr and urine albumin-creatinine ratio • Exclude infection, trauma, bleeding from the distal urinary tract/bladder, menstruation • Consider bleeding disorder

Additional specialized assessments are available to assess renal function or renal pathology.

(Note: In exceptional cases when a nephrologist considers a renal biopsy, it is strongly recommended to make specimen slides available for evaluation by Anthos to potentially identify project-wide patterns of nephrotoxicity.)

Whenever a renal event is identified, a detailed subject history and examination are indicated to identify, document and potentially eliminate risk factors that may have initiated or contributed to the event:

- Blood pressure assessment (after 5 min rest, with an appropriate cuff size)
- Signs and symptoms such as fever, headache, shortness of breath, back or abdominal pain, dysuria, hematuria, dependent or periorbital edema
- Changes in blood pressure, body weight, fluid intake, voiding pattern, or urine output
- Concomitant events or procedures such as trauma, surgical procedures, cardiac or hepatic failure, contrast media or other known nephrotoxin administration, or other potential causes of renal dysfunction, e.g., dehydration, hemorrhage, tumor lysis

Table 8: Follow-up renal events

Action	Follow up
Assess*, document and record in the CRF or via electronic data load. Review and record possible contributing factors to the renal event (co-medications, other co-morbid conditions) and additional diagnostic procedures (MRI etc.) in the CRF	
 • Urine exam and sediment microscopy • Blood pressure and body weight • Serum creatinine, electrolytes (sodium, potassium, phosphate, calcium), bicarbonate, and uric acid • Urine output
Monitor subject regularly (frequency at Investigator’s discretion) until:	
 • Event resolution: (sCr within 10% of baseline or protein-creatinine ratio within 50% of baseline) OR • Event stabilization: sCr level with $\pm 10\%$ variability over last 6 months or protein-creatinine ratio stabilization at a new level with $\pm 50\%$ variability over last 6 months.

*Urine osmolality: in the absence of diuretics or chronic kidney disease this can be a very sensitive metric for integrated kidney function that requires excellent tubular function. A high urinary osmolality in the setting of an increase in sCr will point toward a “pre-renal” cause rather than tubular toxicity.

12.3. Appendix 3 - Clinical notable laboratory values

Clinical notable laboratory values:

The definition, the specific alert criteria and the corresponding actions for hepatic and renal notable laboratory abnormalities are respectively provided in [Appendix 1](#) and [Appendix 2](#).

The following laboratory values are considered clinically notable and should be forwarded to Covance at the same time that they are sent to Investigators:

- A change from baseline in hemoglobin ≥ 2 g/dL
- A decrease from baseline in platelets count $\geq 50\%$ or $< 100 \times 10^9/L$
- A positive fecal occult blood test
- Macroscopic hematuria

Whenever a clinically notable laboratory value is identified, a detailed subject history and examination are indicated to identify, document and potentially eliminate a bleeding event:

- Blood pressure assessment (after 5 min rest, with an appropriate cuff size);
- Signs and symptoms such as shortness of breath, tiredness, abdominal pain, hematemesis, rectorrhagia, melena, gingival or nose bleeding, bruising and hematoma;
- Concomitant events or procedures such as trauma, surgical procedures.

When one of the above occurs the action plan is as follows:

- Confirm the value, assess and document the clinically notable laboratory value in the CRF or via electronic data load;
- Investigate the underlying causes such as clinical or subclinical bleeding event and the contributing factors such as intake of prohibited medications;
- Monitor subject regularly (frequency at Investigator's discretion) until resolution or stabilization. Hospital admission, additional laboratory tests, endoscopy, volume replacement, transfusion, etc. should be performed at the Investigator's discretion and according to the medical needs (see [Section 6.3](#) for reversal therapy).

12.4. Appendix 4 - Schedule of Assessments

Table 9: Schedule of Assessments

Period	Screening	Treatment							Washout / Follow-up			
Visit	1	2	3	4	5	6	7	8	9	10	TD	EoS
Day	-28 to -3	1 (predose)	11	31 (predose)	41	61 (predose)	71	91	101	121	-	170
Window			±2	±2	±3	±2	±3	±2	±3	±3		±10
Informed consent	X											
Medical history	X											
Drug & alcohol screen	X											
I/E criteria	X	X										
Physical Exam	X	X	X	X		X		X		X	X	X
Height	X											
Weight	X	X										X
Vital signs	X	X	X	X	X	X	X	X	X	X	X	X
12-lead ECG	X	X						X				X
HIV, Hepatitis B, Hepatitis C	X											
aPTT, Free and total FXI	X	X	X	X	X	X	X	X	X	X	X	X
aPTT (corrected for FXI), FXI:C		X				X		X				X
PK assessment: total MAA868		X	X	X	X	X	X	X	X	X		X
Antidrug antibodies (ADA)		X		X		X	X	X		X		X
Exploratory biomarker collection	X	X		X		X		X		X		
Complete safety Labs	X	X	X	X	X	X		X		X	X	X
Pregnancy test	Serum	Urine			Urine			Urine			Urine	Urine
Urine	X	X	X	X	X	X		X		X	X	X
Fecal occult blood test	X	X										
AE collection						X						
Concomitant meds						X						
Local assessment of CV and cerebrovascular events							X					
Local assessment of bleeding events							X					
Dispense Study Medications		X		X		X						
Drug Accountability		X		X		X		X				
MAA868		X		X		X						
Placebo		X		X		X						

Period	Screening	Treatment							Washout / Follow-up			
Visit	1	2	3	4	5	6	7	8	9	10	TD	EoS
Day	-28 to -3	1 (predose)	11	31 (predose)	41	61 (predose)	71	91	101	121	-	170
Window			±2	±2	±3	±2	±3	±2	±3	±3		±10
Injection site inspection (post-dose)		X	X	X	X	X	X					
Study disposition								X			X	X

TD = Study treatment discontinuation; EoS = End of Study; FXI:C = Factor XI coagulation activity

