5.7. Study Completion and Post-study Treatment

Each subject will be required to complete the study in its entirety and thereafter no further study treatment will be made available to them.

Study completion is defined as when the last subject completes their EoS visit, and any repeat assessments associated with this visit have been documented and followed-up appropriately by the Investigator, or in the event of an early study termination decision, the date of that decision.

All subjects will be required to attend the EoS visit and have related assessments collected as per the Schedule of assessments (Table 9). All SAEs reported during this time period must be reported as described in Section 7.6.2. and the Safety Management Plan. Documentation of attempts to contact the subject should be recorded in the source documentation.

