5.8. Discontinuation of Study Treatment

The Investigator may decide to suspend the s.c. administration of the study drug if symptoms or signs consistent with an injection site reaction or hypersensitivity reaction occur.

Subjects who decide they do not wish to participate in the study further should NOT be considered withdrawn from the study UNLESS they withdraw their consent (see Section 4.3, Withdraw of Informed Consent). Where possible, they should return for the EoS assessments indicated in the assessment table. If they fail to return for these assessments for unknown reasons, every effort (e.g. telephone, e-mail, letter) should be made to contact the subject/pre-designated contact as specified in Section 4.3 (Lost to follow-up). This contact should preferably be done according to the study visit schedule.

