7. STUDY ASSESSMENTS AND PROCEDURES

7.1. Assessment schedule

Subjects should be seen for all visits/assessments as outlined in the assessment schedule ([Table 9](#)).

Missed or rescheduled visits should not lead to automatic discontinuation. Subjects who prematurely discontinue the study for any reason should be scheduled for a visit as soon as possible, at which time all of the assessments listed for the study treatment discontinuation (TD) visit will be performed.

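### The treatment-discontinuation visit takes no ADA or PK sample, so neither is measured when a subject leaves; adding both to the planned blood draw is a cheap improvement

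*Protocol*

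**What the plan says.** - **Table 9 (Protocol Appendix 4).** The TD column is marked for "aPTT, Free and total FXI", "Complete safety Labs", urine and the pregnancy test. The rows "Antidrug antibodies (ADA" and "PK assessment: total MAA868" are blank there. Both are marked at EoS (Day 170).
- **Protocol 7.1.** A subject who leaves the study early is seen as soon as possible, "at which time all of the assessments listed for the study treatment discontinuation (TD) visit will be performed". Nothing beyond the TD list is required.
- **Protocol 5.7.** "All subjects will be required to attend the EoS visit and have related assessments collected as per the Schedule of assessments".
- **Protocol 5.8.** For subjects who no longer wish to take part: "Where possible, they should return for the EoS assessments indicated in the assessment table".
- **Protocol 7.15.** Residual blood may be used for another protocol endpoint. This is a permission, not a commitment.
- **SAP 4.1.** PK samples are taken and evaluated at every visit after screening, where data permit. TD is not named as an exception.
- **SAP 7.8.9.** ADA results are summarised by scheduled visit and listed by subject. No per-subject incidence is planned.

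**The concern.** Immunogenicity is a secondary objective and part of the trial's title. Protocol 5.8 names hypersensitivity and injection-site reactions as reasons the investigator may suspend dosing, and for such events a concurrent antibody result and drug level help interpretation. Free FXI is drawn at TD. If inhibition is poor there, the plan gives no way to tell low exposure from an antibody effect at that moment. SAP 6.2.2 uses observed data only, so a sample not taken is not replaced.

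Separately, SAP 4.1 and Table 9 disagree on whether PK is taken at TD, and a site following Table 9 will not take it.

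**Working it through.** The plan states no figure on this point, so there is none to reproduce.

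**1. Table 9, row by row.** Each row has exactly 12 cells (Visits 1 to 10, TD, EoS), so the blanks are not a misaligned column.

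| Row | Days marked before TD | TD | EoS |
|---|---|---|---|
| aPTT, free/total FXI | Screening, 1, 11, 31, 41, 61, 71, 91, 101, 121 | X | X |
| Safety labs | Screening, 1, 11, 31, 41, 61, 91, 121 | X | X |
| PK | 1, 11, 31, 41, 61, 71, 91, 101, 121 | blank | X |
| ADA | 1, 31, 61, 71, 91, 121 | blank | X |

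**2. Who has no post-dose result at all.** Day 1 is predose, so the first post-dose samples are Day 11 (PK) and Day 31 (ADA).

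| Subject leaves | EoS attended | EoS missed |
|---|---|---|
| Before Day 11 | ADA and PK at EoS only | Neither |
| From Day 11, before Day 31 | PK from Day 11; ADA at EoS | PK only |
| From Day 31 | Earlier ADA and PK, plus EoS | Earlier ADA and PK |

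No row has a sample tied to the TD visit itself.

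**3. What an EoS sample can replace.** Protocol 1.1 gives a mean terminal half-life of 20 to 28 days (single dose, healthy subjects). As a first-order approximation that ignores absorption and target binding, the share remaining at Day 170 is 0.5^(days since last dose / half-life).

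| Last dose | Days to Day 170 | Half-life 20 d | Half-life 28 d |
|---|---|---|---|
| Day 1 | 169 | 0.29% | 1.52% |
| Day 31 | 139 | 0.81% | 3.20% |
| Day 61 | 109 | 2.29% | 6.73% |

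Across the ±10-day EoS window the extremes are 0.20% (last dose Day 1, EoS Day 180) and 8.62% (last dose Day 61, EoS Day 160). If decay starts only at the latest median Tmax the protocol reports (21 days after dosing), the highest Day 170 figure becomes 0.5^(88/28) = 11.3%. Back-calculating from EoS to the last dose is also imprecise. The half-life range alone moves the answer by a factor of 6.73/2.29 = 2.9 for a last dose on Day 61 and 1.52/0.29 = 5.2 for Day 1. An EoS sample can still show antibodies; it cannot give the drug level at stopping.

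**4. Effect on the planned analyses.** The efficacy endpoints use troughs at Days 31, 61 and 91, so FXI at TD enters none of them. SAP 4.1 derives PK parameters after the Day 61 dose only, so a TD sample before that dose feeds none of them. There is one narrow exception. SAP 4.1.1 needs at least three consecutive quantifiable concentrations for AUC. A subject who leaves after Day 71 and before Day 91 has two, counting the Day 61 predose value, and a TD sample could be the third.

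**5. SAP 4.1 against Table 9.** The SAP lists protocol Version 2.0 as its source, and that version's Table 9 has the same blank TD cells. The later protocol amendment therefore does not explain the disagreement.

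**The case against.** The case against is substantial, and most of it stands.

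- **The data are not generally lost.** A reader might infer that ADA and exposure information disappears for subjects who discontinue. The documents do not support that. Section 5.7 requires EoS of everyone, Section 5.8 does not count a subject as withdrawn unless consent is withdrawn, and Section 4.3 has the investigator carry out whatever visits are still allowed. Earlier samples remain.
- **Stopping treatment is not leaving the study.** Doses are given only on Days 1, 31 and 61. A subject who attends Day 31 or Day 61 and is not dosed has already given predose ADA and PK samples. Suspending dosing under Section 5.8 does not end follow-up.
- **No bias in ADA incidence can be quantified.** A reader might infer that unsampled leavers drop out of the denominator and lower the rate by a calculable amount. SAP Table 1 keeps the analysis-set denominator by default and shows missing as a category. No subject-level incidence is planned, and neither a dropout rate nor an ADA rate is given.
- **The study is descriptive.** No significance tests are planned and no efficacy endpoint is affected.
- **Residual TD blood could be assayed.** Section 7.15 allows this but commits no one to it. Section 10 allows extra assessments needed for safety, case by case, but otherwise bars additional research sampling.

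None of this provides a planned ADA or PK sample at TD, and an EoS sample does not stand in for exposure months earlier.

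**Conclusion.** The point holds as a modest, cheap improvement. The TD visit measures FXI and safety labs but neither ADA nor total MAA868, and no other provision requires them at that visit. Earlier visits and EoS partly cover ADA. They do not give drug exposure at discontinuation.

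Complete absence of post-dose data is confined to subjects who also miss EoS, having left before Day 31 (ADA) or before Day 11 (PK). How many that would be cannot be computed from the documents. That these samples matter most in early leavers is a reasonable judgement, not something the documents state. The residual-drug figures rest on simple first-order decay with the single-dose half-life from healthy subjects; the sensitivity checks above do not change the conclusion.

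The disagreement between Table 9 and SAP 4.1 needs resolving whichever way the sampling question is decided.

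**What to change.** 1. Mark ADA and total MAA868 PK in the TD column of Table 9, drawn at the venipuncture already planned for FXI and safety labs.
2. Reconcile Table 9 with SAP 4.1. If the sponsor decides against PK at TD, SAP 4.1 should name TD as an exception. If residual TD plasma is to be used instead, the protocol should commit to assaying it.
3. Add to SAP 7.8.9 a subject-level summary, by treatment group, of any post-dose ADA-positive result, with TD and EoS included. It should also show how many subjects have no post-dose result. Without this table, a TD result would have no by-visit row of its own and might appear only in listings.

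The cost is two tubes at an existing draw, for early leavers only, with slightly more blood volume and assay work. Placebo PK samples are not analysed under Protocol 7.13, so the added PK assays fall on active-arm leavers. There is also a schedule-table amendment and one extra SAP table.
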